5.3 Principles for Managing Immune Checkpoint Inhibitor Toxicities

The mechanism of sintilimab is to stimulate T-cell activation and proliferation, which may lead to autoimmune disease involving multiple systems. Autoimmune AEs such as immune-related pneumonitis, diarrhea/enterocolitis, renal insufficiency, rash, hepatitis, endocrine disorders, and

peripheral or central neuritis have been observed with checkpoint inhibitors including ipilimumab, nivolumab, pembrolizumab, and atezolizumab. If subjects experienced the irAEs described above, the signs and symptoms should be monitored, relevant examinations should be performed, and the cause should be identified. If an alternative cause is not found (such as PD, concomitant medications, or infections) and glucocorticoids and/or other immunosuppressants are required, then any AE described above is considered related to sintilimab-induced immune hyperfunction, which should be diagnosed as an irAE. Endocrine events such as hyperthyroidism/hypothyroidism, hypophysitis, type I diabetes, and adrenal insufficiency may not require immunosuppressants, but are still considered as immune-related events.

See [Table 4](#) Sintilimab dose adjustments, [Table](#) and the latest NCCN guidelines for management of immune-related toxicity in cancer immunotherapy for dose adjustments and management of toxicity.

5.4 Concomitant Treatments

All concomitant medications will be recorded in the EMR only.

5.4.1 Prohibited treatments

The following treatments are prohibited throughout the trial:

- Any systemic chemotherapy or biotherapy (except for cytokine drugs to treat chemotherapy-induced AEs), as well as herbal and proprietary Chinese medicines, with anti-tumor effects other than sintilimab.
- Immunomodulators, including but not limited to non-specific immunomodulators (such as thymosin, interferon, interleukin, immunoglobulin, and gamma globulin) as well as herbal and proprietary Chinese medicines with immunomodulating effects;
- Radiotherapy to control tumors (palliative radiotherapy is allowed if not directed towards the target lesion, such as radiotherapy for relieving pain from bone metastasis and symptoms of brain metastasis);
- Inoculation with live vaccine within 30 days prior to the first dose of study treatment and throughout the trial. Live vaccines include but are not limited to measles, mumps, rubella, chicken pox, yellow fever, rabies, Bacillus Calmette Guerin, and typhoid (oral) vaccines; Seasonal inactivated influenza virus vaccines are permitted, but live attenuated influenza vaccines are not;

- Corticosteroids. Inhaled steroids for subjects with asthma or chronic obstructive pulmonary disease (COPD) are permitted; temporary use of corticosteroids for dyspnea are permitted; corticosteroids are permitted for the treatment of immune-related AEs; corticosteroids of physiologic dose are permitted after consulting the PI.

Note: Prophylactic corticosteroids as pretreatment of allergic reactions (e.g. premedication prior to IV contrast agent or chemotherapy) are permitted.

Based on the assessment of the investigator, subjects requiring any one of the treatment methods above must be excluded from the trial. Subjects may receive other medications that the investigator considers medically necessary.

It is very important for the investigator to review every drug (prescription and non-prescription) used by the subject prior to the trial and during each visit.

- During each visit, subjects must be asked about any new medications received.
- To minimize the risk of drug-drug interactions, the concomitant medications should be limited to those that are really necessary.
- Drugs with hepatotoxicity (i.e. those with warnings in the prescribing information) should be avoided if possible during the treatment. The investigators are encouraged to review every potential hepatotoxic drug via www.livertox.nih.gov.
- Prohibited drugs listed in the exclusion criteria are not permitted.

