		
mg/kg
 
If failure of improvement after 4 weeks or worsening in meantime, consider synthetic or biologic DMARD
 
Synthetic: methotrexate, leflunomide
 
Biologic: consider anticytokine therapy such as TNF-α or IL-6 receptor inhibitors. (Note: As caution, IL-6 inhibition can cause intestinal perforation; while this is extremely rare, it should not be used in patients with colitis.)
 
Test for viral hepatitis B, C, and latent/active TB test prior to DMARD treatment

Myositis	Grade 1	Continue
	Grade 2	Interrupt until the symptoms are controlled and CK is normal. If CK is elevated three times or more, initiate prednisone or equivalent at 0.5-1 mg/kg.
	Grade 3-4	
Interrupt until resolve to grade 0-1 without immunosuppression; permanently discontinue if there are signs of myocardial involvement.
 
Initiate prednisone 1 mg/kg or equivalent. Consider 1-2 mg/kg of methylprednisolone IV or higher-dose bolus if severe compromise (weakness severely limiting mobility, cardiac, respiratory, dysphagia)
 
Consider plasmapheresis
 
Consider IVIG therapy
 
Consider other immunosuppressant therapy, such as methotrexate, azathioprine, or mycophenolate mofetil, if symptoms and CK levels do not improve or worsen after 4-6 weeks;

Polymyalgia Rheumatica-Like	Grade 1	Continue
	Grade 2	Consider interruption until symptoms are controlled. prednisolone

Drug-Related Toxicities	Severity	Management
Syndrome		< 10 mg;
	Grade 3–4	Interrupt, consult a rheumatologist to decide whether to resume the treatment after resolving to grade 0–1. Initiate prednisone 20 mg/d or equivalent. If no improvement or need for higher dosages for prolonged time, may offer a corticosteroid-sparing agent, such as methotrexate or IL-6 inhibition with tocilizumab
6. Nephrotoxicities		
Nephritis	Grade 1	Consider interruption, make judgment based on other possible causes and the baseline renal function
	Grade 2	Interrupt administer 0.5-1mg/kg/d prednisone equivalents. If worsening or no improvement: 1 to 2 mg/kg/d prednisone equivalents and permanently discontinue treatment. If improved to G1 or less, taper corticosteroids over 4-6 weeks
	Grade 3	Permanently discontinue. Initiate 1 to 2 mg/kg/d prednisone equivalents
	Grade 4	Permanently discontinue, Consult a nephrologist. Administer corticosteroids (initial dose of 1-2mg/kg/d prednisone or equivalent)
Symptomatic Nephritis: Follow-Up	Grade 1	Resume routine creatinine monitoring if resolve to baseline values

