	Grade 2	If resolve to grade 1, taper glucocorticoid dose for at least 3 weeks; If elevations persist. 7 days or worsen and no other cause found, treat as G3
	Grade 3–4	If resolve to grade 1, taper glucocorticoid dose for at least 4 weeks. If elevations persist >3-5 days or worsen, consider additional immunosuppression (eg, mycophenolate)
7. Neurotoxicities		
Myasthenia Gravis	Grade 1 (not applicable)	/

Drug-Related Toxicities	Severity	Management
	Grade 2	Interrupt until resolve. Administer corticosteroids (prednisone, 1-1.5 mg/kg orally daily) if symptoms G2; wean based on symptom improvement
	Grade 3-4	Permanently discontinue. Continue corticosteroids and initiate IVIG 2 g/kg IV over 5 days (0.4 g/kg/d) or plasmapheresis for 5 days
Guillain-Barré Syndrome	Grade 1 (not applicable)	/
	Grade 2-4	Permanently discontinue. Start IVIG (0.4 g/kg/d for 5 days for a total dose of 2 g/kg) or plasmapheresis. Or methylprednisolone 2-4 mg/kg/d, followed by slow corticosteroid taper. Or pulse corticosteroid dosing (methylprednisolone 1 g/d for 5 days) for G3-4 along with IVIG or plasmapheresis
Peripheral Neurotoxicity	Grade 1	Lower the criteria for interruption and monitor the symptoms for 1 week; closely monitor the symptoms if continue the treatment
	Grade 2	Interrupt until resolve to grade 0-1. Initial observation OR initiate prednisone 0.5-1 mg/kg (if progressing from mild).
	Grade 3-4	Permanently discontinue. Initiate IV methylprednisolone 2-4 mg/kg and proceed as per Guillain-Barre' syndrome management.
Autonomic Neuropathy	Grade 1	Lower the criteria for interruption and monitor the symptoms for 1 week; closely monitor the symptoms if continue the treatment
	Grade 2	Interrupt until resolve to grade 0-1. Initial observation OR initiate prednisone 0.5-1 mg/kg (if progressing from mild).
	Grade 3-4	Permanently discontinue. Initiate methylprednisolone 1 g daily for 3 days followed by oral corticosteroid taper.
Aseptic Meningitis	Grade 1-4	Permanently discontinue. Once bacterial and viral infection are negative, may closely monitor off corticosteroids or consider oral prednisone 0.5-1 mg/kg or IV methylprednisolone 1mg/kg if

Drug-Related Toxicities	Severity	Management
		moderate/severe symptoms

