	Grade 2–4	Interrupt resume the treatment after resolving to grade 1. For Grade 2, administer prednisone 1 mg/kg/d (dosage range, 0.5-2 mg/kg/d) orally for 2-4 weeks after which time this medication should be tapered over 4-6 weeks to the lowest effective dose. For Grade 3-4, Prednisone 1-2 mg/kg/d (oral or IV depending on symptoms). If worsening or no improvement, 1-2 mg/kg/d prednisone equivalents and permanently discontinue treatment IVIG used with corticosteroids when a more-rapid increase in platelet count is required If IVIG is used, the dose should initially be 1 g/kg as a one-time dose. This dosage may be repeated if necessary If previous treatment with corticosteroids and/or IVIG unsuccessful, subsequent treatment may include rituximab, thrombopoietin receptor agonists, or more-potent immunosuppression
Acquired Hemophilia	Grade 1–2	Interrupt, For Grade 1, administer 0.5-1 mg/kg/d prednisone; For Grade 2, administer 1 mg/kg/d prednisone 6 rituximab (dose, 375 mg/m ² weekly for 4 weeks) and/or cyclophosphamide (dose, 1-2 mg/kg/d); choice of rituximab v cyclophosphamide is patient specific

Drug-Related Toxicities	Severity	Management
		and should be done with assistance of hematology consult; prednisone, rituximab, and cyclophosphamide should be given for at least 5 weeks
	Grade 3–4	Permanently discontinue. Prednisone 1-2 mg/kg/d (oral or IV depending on symptoms) 6 rituximab (dose, 375 mg/m ² weekly for 4 weeks) and/or (dose, 1-2 mg/kg/d). If worsening or no improvement add cyclosporine or immunosuppression/immunoabsorption
9. Cardiovascular Toxicities		–
Myocarditis, Pericarditis, Arrhythmia, Ventricular Insufficiency with Heart Failure and Vasculitis	Grade 1	Interrupt
	Grade 2–4	Permanently discontinue. High-dose corticosteroids (1-2 mg/kg of prednisone) initiated rapidly (oral or IV depending on symptoms). In patients without an immediate response to high-dose corticosteroids, consider early institution of cardiac transplant rejection doses of corticosteroids (methylprednisolone 1 g every day) and the addition of either mycophenolate, infliximab, or antithymocyte globulin.
Venous Thromboembolism	Grade 1–3	Continue
	Grade 4	Permanently discontinue
10. Ocular Toxicities		
Uveitis/Iritis	Grade 1	Continue

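### Section 5.4.1 bans immunoglobulin throughout the trial with no exception for immune-related AEs, while Table 4 offers IVIG in nine toxicity rows; the two need reconciling.

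*Combined protocol and SAP*

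**What the plan says.** Section 5.4.1 opens its list with "The following treatments are prohibited throughout the trial". One bullet covers immunomodulators and gives examples: "such as thymosin, interferon, interleukin, immunoglobulin, and gamma globulin". That bullet carries no exception. The corticosteroid bullet in the same list does: "corticosteroids are permitted for the treatment of immune-related AEs". After the list comes the consequence, which depends on the investigator's assessment: "subjects requiring any one of the treatment methods above must be excluded from the trial".

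Section 5.2.2, Table 4, sets out the management of sintilimab-related toxicities, and its footnote spells out IVIG as intravenous immunoglobulin. For Guillain-Barré syndrome grade 2–4 it says "Start IVIG (0.4 g/kg/d for 5 days for a total dose of 2 g/kg) or plasmapheresis"; for myositis grade 3–4, "Consider IVIG therapy"; for immune thrombocytopenia grade 2–4, "IVIG used with corticosteroids when a more-rapid increase in platelet count is required". Sections 5.3 and 8.6.1 send staff to Table 4 or to Section 5.2 when such an event occurs.

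**The concern.** The drug banned by name in one section is offered by name in another, for serious events caused by the study drug. Staff treating such an event would find IVIG listed in Table 4 and prohibited in Section 5.4.1, with nothing to say which governs. Different staff could resolve this differently.

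The statistical interest lies in what happens next. If exclusion were handled as withdrawal, a subject's protocol follow-up would end because of a drug-related event. The exposed data would be the 90-day collection of AEs and irAEs and the later follow-up for PFS, DOR and OS.

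**Working it through.** No arithmetic beyond a count applies, so the check sets the texts side by side.

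**1. Is it the same product?** Yes. Section 5.4.1 names immunoglobulin and gamma globulin, and the Table 4 footnote defines IVIG as intravenous immunoglobulin.

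**2. Where does Table 4 name it, and how firmly?**

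| Table 4 row | Grade | How IVIG is offered | Sintilimab |
|---|---|---|---|
| Serious skin reactions | 4 | Optional, alongside cyclosporine | Permanently stopped |
| Pneumonitis | 3–4 | One of several optional additions | Permanently stopped |
| Myositis | 3–4 | To be considered | Interrupted; permanently stopped only with myocardial signs |
| Myasthenia gravis | 3–4 | To be started, or plasmapheresis instead | Permanently stopped |
| Guillain-Barré syndrome | 2–4 | To be started, with plasmapheresis or methylprednisolone as alternatives | Permanently stopped |
| Encephalitis | 1–4 | To be considered with pulse steroids in some cases | Permanently stopped |
| Transverse myelitis | 1–4 | To be strongly considered | Permanently stopped |
| Autoimmune hemolytic anemia | 3–4 | One example among further drugs | Permanently stopped |
| Immune thrombocytopenia | 2–4 | With steroids, when a faster platelet rise is needed | Interrupted and resumed at grade 1; permanently stopped if worse or not improving |

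That is 9 rows. Peripheral neurotoxicity grade 3–4 refers to Guillain-Barré management, which makes 9 + 1 = 10. Of the nine, 7 stop sintilimab permanently, and 9 − 7 = 2 leave resumption open in some circumstances.

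**3. Does other text lift the ban?** Three candidates, none sufficient:
- Section 5.4.1 lets subjects receive other medications judged medically necessary. Read with the list above it, this covers drugs that are not on the list.
- Section 5.4.2 permits medication for treatment-related AEs, but only medication that meets the protocol's requirements. A drug prohibited by name does not clearly qualify.
- Sections 5.3 and 8.6.1 point to Table 4 or Section 5.2, but do not say that these prevail over Section 5.4.1.

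Because the same list gives corticosteroids an express exception for immune-related AEs, silence on immunoglobulin is hard to read as permission.

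**4. Does stopping sintilimab remove the conflict?** No. Section 4.4.1 says that discontinuing treatment is not withdrawing from the study. A subject off sintilimab is still in the trial, and the ban runs for the whole trial.

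**5. What does exclusion mean for the data?** The documents do not settle it.
- Use of a prohibited drug is not among the discontinuation reasons in Section 4.4.1 or the withdrawal reasons in Section 4.4.2.
- Withdrawal under Section 4.4.2 ends protocol follow-up and bars replacement. Discontinuation under Section 4.4.1 keeps data collection going to the last scheduled visit.
- The protocol uses the word loosely elsewhere. Sections 7.2.2.2 and 8.4.3 exclude a subject who becomes pregnant, while Section 4.4.1 lists a positive serum pregnancy test as a reason to stop treatment, after which monitoring can continue.

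**6. Analysis sets (Section 9.2).** ITT is all enrolled subjects who are treated, and the safety set is everyone with at least one dose; receiving IVIG changes neither. The evaluable set needs measurable baseline disease and one restaging, so it could be affected only if a subject left before the first restaging. The per-protocol set drops only major violations that affect the efficacy evaluation, and it serves sensitivity analyses. Nothing classes IVIG for an immune-related AE as such a violation.

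**The case against.** The strongest reply is that this is a missing cross-reference and little more. No row makes IVIG compulsory. The two rows that say to start it both offer plasmapheresis, and most of the rest leave it to judgement. Exclusion depends on the investigator's assessment. A sensible reader would let the specific toxicity instructions prevail over a general list of prohibited drugs.

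Much of that stands. A reader might infer that the two sections cannot both be followed; the alternatives in Table 4 show that they can, by never using the IVIG option. A reader might also infer that sintilimab is routinely resumed after IVIG. The link is loose: the myositis row requires resolution without immunosuppression, and in the thrombocytopenia row the IVIG sentence follows directly on an instruction to discontinue permanently.

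What does not stand is the suggestion that nothing needs changing. An option that the protocol offers in one place and prohibits by name in another is still a contradiction. The rule that the specific governs the general is one the reader has to supply, and leaving exclusion to the investigator means that like cases may be handled differently.

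**Conclusion.** The contradiction is real, bears on the handling of serious toxicity, and should be reconciled. Its extent is nine Table 4 rows plus one by reference, against a ban with no exception for immune-related AEs. On a literal reading, a subject managed as Table 4 allows would have to be excluded under Section 5.4.1.

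Two stronger readings are tempting and are not supported. One is that these subjects are lost to follow-up and so cause informative loss. That would require exclusion to mean withdrawal under Section 4.4.2, which the documents do not say; it is a possible risk only. The other is to put a size on the effect by noting that one subject in 25 is 1/25 = 4%. The documents give no rate for IVIG-treated events, so no expected number follows, and a subject who has already been restaged stays in the response denominator.

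The conclusion rests on reading the named ban as not overridden by the general permissions in Sections 5.4.1 and 5.4.2.

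**What to change.** Reconcile Section 5.4.1 with Table 4 so that one rule applies to immunoglobulin given for an immune-related AE, and make each section refer to the other. Which rule applies is a clinical choice for the sponsor.

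Whatever the choice, state that subjects managed under Table 4 remain in safety and survival follow-up and in the analysis sets whose Section 9.2 definitions they meet. Say also what exclusion in Section 5.4.1 means in the terms of Sections 4.4.1 and 4.4.2: discontinuation of treatment, or withdrawal from the study.

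The cost is a short text amendment, with no effect on sample size, the visit schedule or the planned analyses.

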5.4.2 Permitted treatments

- Medications that meet the protocol requirements, as determined by the investigator (e.g. concomitant medication used for disease-related symptoms and treatment-related AEs);
- Subjects with underlying diseases such as hypertension and diabetes requiring chronic medications can continue these treatments;
- Local surgery or radiotherapy used for isolated lesions (excluding target lesions);
- Supportive care for relieving tumor-related symptoms, such as bisphosphonate treatment for bone metastases;
- Use of corticosteroids by topical administration, such as dermal, ocular, nasal, and inhaled;

- Prophylactic antiviral therapy is permitted for hepatitis B carriers. Refer to treatment guidelines for dosage and administration.

5.4.3 Drug-drug interactions

- Sintilimab: No interaction information is currently available.

5.5 Drug Management

Sintilimab should be refrigerated at 2–8°C in a dry place and away from light. Do not freeze. Cold-chain should be maintained during transport, and the study drug should be maintained and dispensed by a designee.

The study drugs should be stored in a refrigerator only accessible to the authorized personnel. After receiving the study drugs, the investigator should ensure that the temperature during the transport is maintained within the specified range, sign for receipt upon verification, and store the study drugs at the specified temperature. If abnormalities of the storage temperature during either the transport or storage at the study site arise, the study drugs should be moved to an environment in the specified temperature as soon as possible and should not be administered. Notify the sponsor in a timely manner and follow the advice of the sponsor.

All the study drugs provided by the sponsor should only be used for this clinical trial. Any purposes other than those specified in the protocol are not permitted. The investigator must agree not to provide the study drugs to any patients not in the trial.

5.5.1 Return and destruction

Upon the completion or discontinuation of the study, all unused or expired study drugs will be destroyed locally in accordance with all applicable institutional standard operating procedures, local and federal laws.

5.6 Study Drug Records

The designee of the study site(s) should keep accurate and complete records for receiving, dispensing, using, storing, returning, and destroying study drugs in accordance with the relevant regulations and guidelines and the operational requirements of this study.

6 Study Procedure

6.1 Enrollment

6.1.1 Enrollment

All protocol participants will be registered in Clinical Oncology Research System (OnCore/CORe) websit. The investigator will enroll subjects using the following steps:

1. Obtain the ICF signed by the subjects prior to any study-related procedures;
2. Confirmation of the subjects' eligibility by the principal investigator or trained designee after reviewing the inclusion/exclusion criteria;

Subjects who do not meet the criteria (screen failures) may be re-screened. If re-screening is considered, the investigator must contact the study PI. Each subject can be re-screened once. The subject must sign the ICF again and be assigned a new identification number when re-screening.

6.1.2 Enrollment error handling

The inclusion/exclusion criteria must be followed strictly. If an ineligible subject is enrolled, the sponsor's medical monitor and investigator must discuss whether the subject is allowed to continue the study and whether the subject can be treated with the study drugs. If it is determined by the investigator that allowing the subject to continue the study is medically appropriate and this is agreed to by the sponsor's medical monitor, then the subject will continue the study and receive the study drugs. On the other hand, if the investigator/IND does not agree, the subject should not continue the study (regardless of receiving the study drugs or not).

6.2 Study Plan and Schedule

6.2.1 Screening

The following procedures must be completed during the screening (Day -28 to -1) to ensure subject eligibility:

- Signing the ICF
- Confirming the inclusion/exclusion criteria
- Recording the demographics, medical history, and prior medications
- Recording the vital signs, height, and weight
- Physical examination

- ECOG PS
- 12-lead ECG (within 7 days prior to the first dose)
- Complete blood count/blood biochemistry/routine urinalysis (within 7 days prior to the first dose)
- Coagulation function (within 7 days prior to the first dose)
- Pregnancy test (where applicable within 3 days prior to the first dose)
- Thyroid function (results obtained within 28 days prior to first dose)
- HIV antibody, hepatitis B panel (test HBV DNA for subjects with positive HBsAg), and HCV antibody (test HCV RNA for subjects with positive HCV antibodies). Results obtained within 28 days prior to first dose are also accepted.
- AE evaluation
- Concomitant medications
- Tumor imaging evaluation
- Archival or fresh tumor tissue

Refer to Sections [7.1](#) and [7.2](#) for details regarding tumor evaluation and safety evaluation.

